participants' experiences using the test. Those randomized to a study condition during the study phase will be mailed HBST test kits to their home addresses, which will be stored in a database hosted on Brown University's secure internal servers, password-protected, and can only be accessed from computers physically located at the research offices. A unique link will also be emailed to participants each month over the course of the study to facilitate completion of monthly assessments. Screening, baseline, and monthly assessment data will be stored according to protocols for handling sensitive information, and we will destroy all identifying information after the study is completed. Participants will be compensated based on completion of study appointments, monthly assessments, and follow-up interviews. Focus group participants ($N=8$) will be paid \$50. Individual interview participants ($N=10$) will be paid \$30. Participants will be paid \$20 for completing the baseline in-person appointment and \$15 per monthly assessment (\$105 total), with a \$55 bonus for completing all assessments on time (within +/- 5 days of being assigned). This compensation schedule is consistent with standard reimbursement amounts for research involvement at the Center for Alcohol and Addiction Studies at Brown University, thus posing little risk of coercion. Payments will be issued in cash. Recruitment and compensation procedures have been approved by the Brown University Research Protections Office IRB.

Informed Consent. The informed consent process will be conducted by trained staff members that possess research experience working with the target populations and who are also trained in the ethical treatment of human subjects. Staff members will also be trained in more advanced research topics, such as protocol adherence, quality assurance, data management, and so on. The process of informed consent involves presenting a detailed verbal description of the study as it is described on the printed, IRB-approved consent form. Staff will emphasize that participation is voluntary, and that participants can refuse to answer any question and/or can discontinue participation at any time without penalty. Interviewers will ask whether participants have experienced any coercion to take part in the study; those that describe any pressure or coercion to participate will be excluded. Potential subjects receive an item-by-item reading of the consent form by the study staff. Participants will be informed of the procedures for ensuring their confidentiality, including: the use of unique non-personally identifying ID numbers instead of names on research materials, and maintenance of data on secure computers, devices, and servers. Compensation for participation will be explained. All participants will be given the contact numbers of the Principal Investigators and Research Protections Office to answer questions about the study or one's rights as a human subject as well as a research site contact number. All consenting participants will be offered a copy of the informed consent form.

D.2 Procedures to Protect Against Risk

Several measures will be implemented to protect against the loss of privacy and/or confidentiality. First, digital audio recordings from focus groups and phone interviews will be stored in a locked cabinet in a locked office until they are transcribed, which will take place no longer than a week after they are collected. No participant identifiers will be associated with these recordings, and prior to conducting the interviews/focus groups, participants will be asked to refrain from providing any information that could identify them. Once transcribed, original voice recordings will be destroyed, and any identifying information provided during the interview will be edited out of transcripts by RAs. Transcript files will be stored in secure, password-protected files on Brown University's servers. Handwritten notes collected by staff during focus groups/individual interviews will also contain no identifying information, and will

be stored briefly in a locked file cabinet in the Investigators' offices until they can also be transcribed (no longer than a week after they are generated), and then destroyed.

Screening, baseline, and monthly assessment data collected online will be stored briefly via Qualtrics© web survey software in de-identified format, before being downloaded weekly and stored in de-identified, password-protected files on Brown University's secure servers. Participant identifying information will be kept in a separate database from study data, in a password-protected file that contains only their unique study ID. Data facilitating monitoring (e.g., participant first names, contact phone number) will be stored in a database that is centrally hosted on Brown University's secure internal servers, and password-protected so that only essential study staff have access. Sensor and BLE ID numbers are not identifiable, and the participant-side mobile app will only be used to relay this information to the centrally-stored database on Brown's servers. As such, the participant-side mobile application will not store any participant data. After being linked with participant IDs in the secure centrally-hosted database a notification and calendar event will be created to let QHTCs who regularly monitor the database know that they need to conduct a follow-up call with participants. These follow-up calls will be conducted in private offices available at Brown University. HBST test kits will be mailed to participants in discreet packaging and participants will be trained to look for these at 1-week, 3-months, and 6-month intervals. They will also be provided with tips for allowing maximum privacy when opening and taking the test. Participants will also be instructed about how to properly dispose of any tests they take, and OraSure's® test kit provides packaging for discreet and safe disposal. When conducting follow-up calls, QHTCs will first ensure that participants have adequate privacy to discuss the test over the phone, and if not, follow-up calls will be re-scheduled. Finally, while monthly email notifications providing the link for monthly assessments will contain no identifying information or other data, participants will be instructed to delete these emails after they have completed their assessment.

Several measures will also be employed to minimize psychological discomfort or distress as a result of the research. First, while participants may experience some discomfort while taking an HIV test at home, past research suggests that this risk is low⁴²⁻⁴⁴, and OraSure's clinical trial data suggests that HBST can be completed safely, resulting in minimal distress. The FDA has also deemed that this product can be used safely by the general public. Nevertheless, participants in either condition will be encouraged to report any distress they experience as a result of testing to study staff, who will provide referral to LGBT-friendly treatment providers in the local area. Second, while some participants may receive "reactive" results during the study, staff will prepare them for this during their orientation visit and encourage participants to interpret this merely as "reactive" (rather than "positive"), since further testing is needed to confirm "positive" results. Participants in either condition will also be encouraged to report receiving "reactive" results to study staff as soon as possible, and will be provided with contact information for doing so. These participants will then be scheduled for confirmatory testing appointments at MIC, which has established procedures for conducting follow-up testing and engaging these patients in care. Finally, the risk of distress or discomfort from study assessments is low, but participants will again be encouraged to report this to study staff as soon as possible. Staff will then provide referrals to local MSM-friendly treatment resources and emergency services. In addition, research staff will be trained in responding to adverse events, including participant distress. These events will be reported promptly to the Brown University IRB.

Finally, to ensure that *all* participants are encouraged to seek follow-up testing and care after testing, participants indicating that they have taken a test on the monthly assessment (either

provided by us or from another clinic) will be asked what the results of this test were. If it was reactive or positive, we will ask whether confirmatory testing has been completed or is pending and whether participants are currently under the care of a physician who is attending to these issues. For those noting having received a “reactive” result from a study test, who is not pursuing confirmatory testing and/or is not under the care of a physician who is aware of this issue, we will follow-up with these participants as soon as possible over the phone. The monthly assessment data will only contain participants’ unique study ID numbers, and will not be identifiable until it is downloaded and imported into the study databases. We will download and monitor the study monthly survey data every 48 hours, and for every participant with this constellation of responses, we will follow up with them over the phone to offer to make appointments with them for confirmatory testing and follow-up care.

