Experimental conditions. In this 7-month longitudinal study, 40 participants will be randomized to receive either “enhanced” HBST ($N=20$) or standard HBST ($N=20$). All will have 3 OraSure® test kits shipped to their homes 1-week after baseline, 3-months, and 6-months. Those in the “enhanced” HBST condition will receive follow-up calls within 24 hours after opening their tests. Those in standard HBST will be provided contact information for local services in their test kits, in addition to the information provided by OraSure®.

Measures. Demographics, past HIV testing history, sexual behavior, and other relevant variables will be collected at baseline. Throughout the 7-month study period, participants will complete online assessments each month inquiring about whether they used a study-provided HBST kits in the last month and what the result was. Items will also assess whether they were provided referral to a local agency for additional prevention services (e.g., additional HIV testing, STI testing, PrEP consultation, HIV risk reduction counseling) by a professional in the last month, and whether they sought each service over the last month. Participants will also complete Timeline Follow Back (TLFB^{55,56}) assessments of their sexual behavior over the past month. The TLFB has proven to be one of the more reliable and valid assessments available for sexual behaviors⁵⁷⁻⁶⁴, and recent evidence suggests that optimal accuracy in reporting may be achieved with short follow-up periods (e.g., 30 days)⁵². Monthly online assessments will also measure general positive/negative affect over that time using the positive and negative affect scales of the PANAS-X⁶⁵, a 20-item scale that asks participants to rate various emotion words according to the extent they have “felt this way over the past month,” on a 1 (*very slightly*) to 5 (*extremely*) scale. These subscales have excellent psychometric properties when used to measure trait affect⁶⁵. Health empowerment will be measured each month using the Patient Activation Measure (PAM-13⁶⁶), and social support will be assessed with 3 subscales of the Received Support Scale (Emotional, Informational, Satisfaction). Both measures have excellent psychometric properties⁶⁶⁻⁶⁹.

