Procedure. See Figure 3 for study timeline. Interested participants will be screened online, and those eligible will be contacted by a research assistant (RA), who will schedule an in-person appointment to begin the study. At this appointment, participants will complete baseline measures and be oriented to the study. In the “enhanced” HBST condition, participants will be informed that sensors will accompany their HBST kits and to expect a call from study QHTCs within 24 hours after opening them, should they choose to test. Study software will then be downloaded onto the participant’s phone, and they will be instructed to keep their Bluetooth feature enabled at all times and to

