keep their phone near them as much as possible over the 7-month study. They will also be instructed to inform study staff as soon as possible should they lose their phones, change phones, or their current service contract lapses. One week after the initial appointment, an HBST kit will be sent to participants’ verified addresses. Shipment tracking will be used to record data about when HBST participants receive their tests. In “enhanced” HBST, participants, opening their mailed test enclosure will trigger an alert on the study database, which is monitored regularly by staff QHTCs. These alerts will instruct QHTCs to conduct a follow-up call with participants. QHTCs will be CAAS postdoctoral trainees with Ph.D.’s in clinical psychology who have completed additional training in HIV testing counseling (offered by [name]), suicide prevention intervention (offered by nearby Lifespan Hospital), and study-specific follow-up procedures. QHTCs will take turns placing follow-up calls. QHTCs will conduct calls while in private offices on Brown University’s campus. As such, they will be able to access the study database while conducting the calls, so as to allow check-ins about previous referrals and data entry during calls. QHTCs will follow up with participants within 24 hours after the test is opened. During follow-up calls, QHTCs will verify whether the participant has completed the test, what the result was, and ask whether the participant would like to receive counseling, entering this data into the study database. For reactive results, QHTCs will facilitate appointments for confirmatory testing. For non-reactive results, QHTCs will inquire about participants’ interest in other prevention services (e.g., STI testing, counseling). QHTCs will also screen for suicidality and record this information using the data entry forms, providing intervention/referral if needed. If participants indicate they have not taken the test yet but plan to do so, QHTCs will ask when they plan to take the test and whether there is a better time to contact them again. If a participant cannot be reached during the 24-hour post-test window, the 3 additional follow-up attempts will be made over the following 72 hours. This process will repeat for tests sent at 3 and 6 months. To facilitate monthly study assessments, participants will receive an email with a link to an each assessment specific to that participant and time period. Participants will be asked to complete these on a desktop computer within 2 days of receipt, and failing to do so within that time will prompt the RA to follow up via phone and email to encourage adherence. Once the study is complete, the RA will follow-up with participants over the phone to conduct a 30-minute qualitative interview. This interview will assess participants’

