Participants will be recruited from the community using ads in popular gay social networking mobile apps (e.g., Grindr, Jackd, Scruff). Participants expressing interest in the study will be screened online. Those meeting eligibility criteria will be contacted by phone and email to schedule an in-person appointment to begin the study. Next, participants will complete baseline measures online. Then, participants will be randomized to a condition. For those in the "enhanced" condition, RAs will inform participants about the study's purpose and guide them in downloading study software onto their smartphones. Although participants will not need to actively provide any input through the app, RAs will instruct participants to keep the app installed, their Bluetooth sensor enabled, and their phones near them throughout the 7-month study. RAs will also ask participants to notify them as soon as possible if they lose their phone or get a new one, their data is erased, or if their service plan changes. Next, RAs will inform all participants that they should expect to receive an email each month with a unique link, and that clicking this link will allow them to complete their monthly assessments. They will also be informed that HBST kits will be mailed to them 1 week after their appointment, and then again in 3 months and 6 months, which they can choose to take or not. However, should they choose to do so, those in the "enhanced" condition will be told that they should expect a call from a QHTC associated with the study within 24 hours after opening their test, and that these calls are intended to provide counseling and referrals after taking the test (which participants can refuse). Finally, participants will be asked to complete a 30-minute follow-up interview about the study via phone after completing the study. They will be informed that they can pick up payments for completing study assessments at the research offices anytime during or after the study.

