2. Participant-side mobile application, will use the Bluetooth sensor on the participant’s smartphone to relay the unique code of the BLE and its state (open, closed) to a database hosted on Brown servers.
3. Centrally-hosted database, which will store minimally-identifying data about participants that is needed to facilitate follow-up, links this information with BLE UUID’s via participants’ unique study ID numbers, and listens for changes in the state of these BLE UUIDs to “push” relevant information to the research-side mobile application.

The BLE will only transmit its unique code (UUID) and the state of its sensor (open, closed) to the participant-side mobile app, and is not identifiable. The participant-side mobile app only “listens” for a change in the BLE’s state, and transmits this data and the beacon’s UUID to the centrally-hosted database. Given this, this data is also not identifiable, and will be stored only briefly via the device’s internal memory until it is relayed, and then erased. **The app itself will only consist of a splash screen with the School of Public Health logo on it, and will be named “Test Helper.”** The centrally-hosted database will use Filemaker, and will be used to store minimally-identifying data (e.g., unique study ID, first name, phone number) about participants for the purposes of conducting monitoring and follow-up. The database will also be used to link incoming data (UUIDs, sensor state) with participant data (via unique study ID numbers), and to provide notifications/scheduling to QHTCs who need to conduct follow up calls to participants. The database will also provide a front-end that facilitates data entry by QHTCs as they are conducting follow-up. This database will be hosted on Brown University’s secure servers and password protected, so that only essential research staff will have access.

Finally, a separate database containing participants' full contact information (including address) and a unique linking ID number will be stored in a separate location on Brown's internal servers. This database will be used by RAs to ship HBSTs to the addresses participants have provided. It will be password-protected and only accessible to essential research staff via computers physically located in the research offices. This database will contain no other study data, and can only be linked with other study data via a linking ID.

D. Risks to Participants and Procedures to Protect Against Risk

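### The enhanced-arm phone link is set up once and not checked before kits 2 and 3, so a dead link looks like an unopened kit and the feasibility count cannot separate the two

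*Protocol*

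**What the plan says.** The Procedure paragraph of Protocol C.4 (Phase II) places set-up at the baseline appointment: "Study software will then be downloaded onto the participant’s phone, and they will be instructed to keep their Bluetooth feature enabled at all times". Participants are then "instructed to inform study staff as soon as possible should they lose their phones, change phones, or their current service contract lapses". Section C.5 repeats the arrangement ("RAs will also ask participants to notify them as soon as possible if they lose their phone or get a new one") and adds erased data and changes of service plan to what should be reported. Neither list asks a man to report that Bluetooth has been off or that the app has been removed, although he is told to keep both in place.

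Kits go out three times: "All will have 3 OraSure® test kits shipped to their homes 1-week after baseline, 3-months, and 6-months". For the later kits the Procedure says only: "This process will repeat for tests sent at 3 and 6 months".

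The call depends on a single event: "opening their mailed test enclosure will trigger an alert on the study database, which is monitored regularly by staff QHTCs". Section C.5.1 describes the app as passive: "The participant-side mobile app only “listens” for a change in the BLE’s state". It gives the participant nothing to look at that would show its status: "The app itself will only consist of a splash screen with the School of Public Health logo on it".

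For Aim 1, the Planned Analyses paragraph looks at the number of successful phone contacts. It does not set that number against kits opened or alerts received. The SAP's list of key outcomes contains no delivery measure.

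**The concern.** A call at 3 or 6 months needs the same phone (or a re-linked one), the app still installed and Bluetooth on. If any of these fails, no alert arrives. Staff see exactly what they would see if the man had left the kit unopened. Shipment tracking does not help, because it records receipt and not opening. Completing a monthly survey does not help either, because participants are asked to do it on a desktop computer.

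Two things are at stake. The first is delivery: a man whose link is dead opens his kit and gets no call, so for that kit he has in effect standard HBST, without the counselling and referral that Aims 2b and 2c compare. The second is interpretation: feasibility is part of the study's stated primary goal, and a low number of contacts at kits 2 and 3 could mean that men did not test or that the system stopped working. Those two readings lead to different next steps.

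**Working it through.** The plan gives no figure to reproduce: there is no expected link-loss rate, and N = 40 is justified as exploratory, without a power calculation. The check has three parts.

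**1. Is there a check anywhere?**
- Set-up: baseline appointment only (C.4 Procedure; C.5).
- Kits 2 and 3: the same process repeated, with no test signal, re-pairing or staff query described.
- App: relays a change of sensor state; no periodic signal described (C.5.1).
- Monthly survey: asks about kit use (C.4 Measures), but no section plans to compare the answers with the alerts. The one described action on the survey data is a call to men with a reactive study test who lack confirmatory testing or care (D.2).
- Start-up interviews: men are asked to use the kit within 1 week (C.4 Phase I), so they do not test whether the link lasts 3 or 6 months.

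**2. How many kits are exposed?**
- Enhanced-arm kits: 20 × 3 = 60.
- Kits 2 and 3: 20 × 2 = 40, or 40/60 = 67%.

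The loss rate has to be assumed. Let *m* be the monthly probability of a permanent, unreported loss, and take the link to be 3 months old at kit 2 and 6 months old at kit 3. The share dead is 1 − (1 − *m*)^3 and 1 − (1 − *m*)^6.

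| *m* (assumed) | Dead at kit 2 | Dead at kit 3 | Untriggered calls if all 40 later kits are opened |
|---|---|---|---|
| 2% | 1 − 0.941 = 5.9% | 1 − 0.886 = 11.4% | 1.2 + 2.3 = 3.5 |
| 5% | 1 − 0.857 = 14.3% | 1 − 0.735 = 26.5% | 2.9 + 5.3 = 8.2 |

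Kit 1, with a link about a week old, adds only 0.1 to 0.3 calls.

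**3. Does this carry over to repeat testing?** The SAP requires tests in at least two of the three intervals. For illustration, assume that a kit is used with probability 0.4, rising to 0.7 if the last kit used was followed by a call.
- Standard arm: 3 × 0.4² × 0.6 + 0.4³ = 0.352.
- Enhanced arm, all links working:
  - kits 1 and 2 used: 0.4 × 0.7 = 0.280
  - kits 1 and 3 only: 0.4 × 0.3 × 0.7 = 0.084
  - kits 2 and 3 only: 0.6 × 0.4 × 0.7 = 0.168
  - total 0.532
- Enhanced arm, 5% monthly loss: 0.520.
- Enhanced arm, every kit-2 call lost: 0.280 + 0.084 + 0.6 × 0.4 × 0.4 = 0.460.

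The kit-2 call enters only the third term, that is, men who skipped kit 1. The kit-3 call enters none. At 5% loss the contrast falls from 0.180 to 0.168. Power with 20 per arm (two-sided 0.05, normal approximation) falls from about 20% to 18%. With use probabilities of 0.5 and 0.8 the pattern is the same: 0.680 falls to 0.668, against 0.500 in the standard arm.

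**The case against.** Several points on the other side stand.

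- **Repeat testing.** A reader might infer that lost links undermine repeat testing, since the later kits are the ones on which it depends. The documents do not support this. The call that can prompt use of kit 2 follows kit 1, when the link is newest. A man who used kits 1 and 2 already meets the SAP definition.
- **Sample size.** A reader might turn the average loss at kits 2 and 3 (about 9 to 20%) into a need for 1/(1 − 0.086)² = 1.2 to 1/(1 − 0.204)² = 1.6 times as many men. That assumes the effect shrinks in proportion to lost calls and leaves out kit 1. Aims 2b and 2c compare numbers of participants, so a man counselled after kit 1 still counts. The plan sets no power target to inflate.
- **Detection.** It would be too strong to say that nothing reveals a failure. Men are told to expect a call within 24 hours, surveys record kit use, and the exit interview covers usability of the monitoring. Detection is delayed, though, and no action on it is planned.
- **Reactive results.** Section D.2 provides backstops in both arms: men are encouraged to report such results and given contact information, and survey data are reviewed every 48 hours.
- **The assumed rates.** Some losses would be reported, Bluetooth can be switched back on, and not every later kit will be opened. The 3 to 8 calls are therefore not a forecast.
- **Loss is itself a finding.** Link attrition under ordinary upkeep is part of what a feasibility pilot should learn. This is true only if it is measured, and at present it is not.

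The protocol also cites a sensor section and an attached funding proposal that were not supplied. A check could be described there.

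**Conclusion.** The concern holds for delivery and for the reading of feasibility. On the supplied documents, the link behind 40 of the 60 enhanced-arm kits is maintained by self-report alone, and a dead link cannot be told from an unopened kit in real time. Each lost link removes that kit's counselling and referral call and leaves Aim 1's contact count ambiguous. Under an assumed permanent, unreported loss of 2 to 5% per month, 6 to 14% of links are dead at kit 2 and 11 to 27% at kit 3, or about 3 to 8 untriggered calls if every later kit is opened.

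It does not hold as a threat to the repeat-testing comparison. There the effect is about one percentage point at 5% monthly loss, under the use probabilities assumed above. This is a worthwhile, inexpensive improvement and not a flaw that invalidates the design.

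**What to change.** 1. In the enhanced-arm surveys that precede kits 2 and 3, ask three yes/no questions: is the phone the same, is Test Helper still installed, is Bluetooth on? The RA resolves any 'no' before the kit is mailed and records what was found.
2. Match survey-reported use of study kits to alerts in the study database.
3. For Aim 1, report the share of links lost as found, before repair, and calls completed per kit opened, by kit number.

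The cost is three items on two surveys already being sent, an occasional RA contact, and a match of data already collected. The downside is slight extra contact in one arm and upkeep somewhat better than in routine use. Asking only before kits 2 and 3, and reporting loss before repair, keeps both small.
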